5.1.9.2 Technical Computational Details for the Analysis of the Exploratory Efficacy Endpoints

- 1) In Treatment Phase A, subjects achieving an increase in serum sodium concentration of ≥ 4 mEq/L (mmol/L) by end of Day 2 (or 2a) will be defined as responders. If subjects do not achieve an increase in serum sodium concentration of ≥ 4 mEq/L (mmol/L) by end of Day 2 (or 2a), they will be defined as nonresponders.
- 2) The QoL GCS scale consists of 23 items encompassing physical, emotional, social, and school domains.

For ease of interpretability, items are reversed scored and linearly transformed to a 0 to 100 scale, so that higher scores indicate better HRQOL (Health-Related Quality of Life).

To reverse score, transform the 0 to 4 scale items to 0 to 100 as follows: 0 = 100, 1 = 75, 2 = 50, 3 = 25, 4 = 0.

To create scale scores, the mean is computed as the sum of the items divided by the number of items answered (this accounts for missing data). If more than 50% of the items in the scale are missing, the scale scores should not be computed. If 50% or more items are completed, then impute missing scores by the mean of the completed items in a scale.

To create the Psychosocial Health Summary Score, the mean is computed as the sum of the items divided by the number of items answered in the Emotional, Social, and School Functioning Scales. The Physical Health Summary Score is the same as the Physical Functioning Scale Score.

To create the total scale score, the mean is computed as the sum of all the items divided by the number of items answered on all the scales.

Child self-reported data for subjects with age ≥ 5 years will be used in the analysis, while for subjects with age < 4 years, parent-reported data will be used.

- 3) The QoL MFS scale consists of 18 items in 3 subscales: general fatigue, sleep/rest fatigue, and cognitive fatigue.

Items are reversed scored and linearly transformed to a 0 to 100 scale as follows: 0 = 100, 1 = 75, 2 = 50, 3 = 25, 4 = 0.

To create scale scores for each dimension, the mean is computed as the sum of the items divided by the number of items answered.

The total QoL MFS score will be calculated by summing up all the items divided by the number of items answered on all the scales.

If more than 50% of the items in the scale are missing, the scale scores should not be computed. If 50% or more items are completed, then impute missing scores by the mean of the completed items in a scale.

Child self-reported data for subjects with age ≥ 5 years will be used in the analysis, while for subjects with age < 4 years, parent-reported data will be used.

- 4) Missing urine concentrations or volumes will not be imputed. All calculations will use nominal times.

If urine volume during a collection interval is zero, then the amount excreted for that interval will be set to missing; values for 24 hours will be determined.

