### **3.7.1 Schedule of Assessments**

#### **3.7.1.1 Screening**

The procedures listed below will be performed during the Screening Visit (Days –2 to –1) to ensure that the subject qualifies for the trial.

- 1) Trial procedures and information regarding the nature of the trial will be reviewed and written informed consent/assent will be obtained prior to any trial-related procedures.
  - a) Informed consent will be obtained from each subject's parent/legal guardian or legally acceptable representative prior to any trial procedures being conducted.
  - b) Each subject who is able will indicate willingness to participate in the trial by signing or marking an assent form (as applicable) supplied for this purpose.
- 2) Inclusion and exclusion criteria will be reviewed.
- 3) Demographic information will be collected.
- 4) Medical and hyponatremia history will be recorded.
  - a) Medical history should include the subject's current list of medical problems that impacts the subject's current hospital stay.
  - b) The hyponatremia medical history should include the etiology of subject's hyponatremia (see [Section 3.3.1](#)) and what treatment was administered prior to trial enrollment. A detailed history specific to etiology of hyponatremia will also be recorded.
  - c) Any observable symptoms of hyponatremia will be assessed and recorded.
- 5) Vital signs (blood pressure, heart rate, respiratory rate, and temperature) will be assessed after the subject has been supine for  $\geq 3$  minutes. Vital signs should be assessed prior to blood draws.
- 6) A resting 12-lead electrocardiogram (ECG) will be performed after the subject has been supine and at rest  $\geq 10$  minutes.
- 7) Body height and weight will be measured. Growth percentiles will be recorded.
- 8) The initial physical examination should be a full physical. Subsequent physical examinations can be directed physical examinations that are focused on hyponatremia-related signs and symptoms as well as any major changes from baseline.
- 9) Tanner staging will be performed.
- 10) A neurological examination will be performed.
- 11) Quality-of-life (QoL) assessment will be performed, as appropriate by age and where available.
- 12) Clinical status assessments will be performed per inpatient standard of care, eg, subject chart entries will be reviewed (including hyponatremia assessment notes, including laboratory results [trial and nontrial specific], any examination findings,

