### **3.7.2.3      Quality of Life Assessments**

Two patient-reported outcomes instruments (acute versions with 7 day recall period) will be used to assess subject quality of life: PedsQL Generic Core Scale and PedsQL Multidimensional Fatigue Scale. Both instruments are appropriate for  $\geq 2$  years of age, however availability may be limited for certain ages and languages. The age groups covered by these assessments are Toddler (2–4 years), Young child (5–7 years), Child (8–12 years), and Adolescent (13–18 years). Depending on the subject's age, the questionnaire may be completed by either the subject, subject and parent/caregiver, or the parent/caregiver, as appropriate.

The PedsQL Generic Core Scale consists of 23 items encompassing physical, emotional, social, and school domains.

The PedsQL Multidimensional Fatigue Scale consists of 18 items in 3 subscales: general fatigue, sleep/rest fatigue, and cognitive fatigue. The instrument focuses on the domains of processing speed, attention/vigilance, visual and working memory.

The assessment time points are at screening, Day 4 and 7 days post-last dose.

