5.1.9 Exploratory Efficacy Analysis

5.1.9.1 Analysis of Exploratory Efficacy Endpoints

Exploratory analyses will include:

- Change in Serum Sodium level from baseline at the end of Treatment Phase B compared to the end of Treatment Phase A for nonresponders continuing on tolvaptan therapy
- Quality of life (QoL) assessments
- In all subjects, 24-hour excretion of sodium, creatinine, and osmolality on Days 1 and 2
- 24-hour sodium clearance on Day 1

A paired Student's t-test will be applied to the change from baseline in serum sodium concentration for nonresponders continuing on tolvaptan therapy.

The QoL assessment includes the PedsQL Generic Core Scale (QoL GCS) and PedsQL Multidimensional Fatigue Scale (QoL MFS). For the QoL GCS, the change from baseline in QoL GCS total score, physical health summary score, and psychosocial health summary score will be analyzed by the paired Student's t-test for the responders. For the

QoL MFS, the QoL MFS total score will be analyzed by the paired Student's t-test for the responders.

For the responders, the change from baseline at the end of Treatment Phase A to the end of the Treatment Phase B will be compared between the Early Withdrawal group and the Late Withdrawal group using the same MMRM analysis that is used for the primary endpoint.

Urine osmolality and urine creatinine, potassium, and sodium concentrations will be summarized by collection interval and for zero to 24 hours on Days 1 and 2 in Treatment Phase A using descriptive statistics.

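### The SAP's quality-of-life reporter rule assigns no source for children aged 4 to under 5

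*SAP*

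**What the plan says.** Protocol 7.4.3 gives no analysis rule for quality of life and leaves it to the SAP. Protocol 3.7.2.3 describes the instruments: "The age groups covered by these assessments are Toddler (2–4 years), Young child (5–7 years"), with Child and Adolescent forms above that. It sets no age at which the reporter changes. Depending on age, "the questionnaire may be completed by either the subject, subject and parent/caregiver, or the parent/caregiver, as appropriate". It also fixes the schedule: "The assessment time points are at screening, Day 4 and 7 days post-last dose".

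SAP 5.1.9.2 then selects the score for analysis. Under item 2, for the Generic Core Scale, the child's own report "for subjects with age ≥ 5 years will be used in the analysis, while for subjects with age < 4 years, parent-reported data" is taken. Item 3, for the Multidimensional Fatigue Scale, ends with the same split: "while for subjects with age < 4 years, parent-reported data will be used".

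SAP 5.1.9.1 names four scores to be analysed in responders: the total, physical and psychosocial scores of the core scale, and the total fatigue score. SAP 5.1 states that, because enrollment was extremely low and the trial ended early, the efficacy analyses need not be done beyond summary statistics.

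**The concern.** A reporter rule should give each child exactly one source. Here the self-report condition starts at 5 and the parent-report condition stops at 4, which leaves a year of age between them. The protocol does not close the gap: it places a 4-year-old on a form but leaves open who completes it, so the SAP rule is the only text that selects the score.

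These children belong to the planned population. The trial enrolls from 4 weeks to under 18 years, and Protocol 3.3 asks for at least 25% of subjects under 6.

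At stake is whose scores enter the summaries that remain. A programmer who applies the rule as written omits collected data for these children. One who notices the gap has to choose a source with no stated rule, possibly after seeing the data.

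**Working it through.** The plan states no figure on this point, so there is nothing to reproduce. The check is to apply the rule to every age that the instruments cover in this trial.

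**Inputs.** Self-report if age ≥ 5 and parent report if age < 4 (SAP 5.1.9.2, items 2 and 3). Forms by age, and use from age 2 (Protocol 3.7.2.3). Upper age limit under 18 (Protocol 3.4.2).

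| Age, completed years | Form | Age ≥ 5? | Age < 4? | Source |
|---|---|---|---|---|
| 2 | Toddler | no | yes | parent |
| 3 | Toddler | no | yes | parent |
| 4 | Toddler | no | no | none |
| 5–7 | Young child | yes | no | self |
| 8–12 | Child | yes | no | self |
| 13–17 | Adolescent | yes | no | self |

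Exact age gives the same result. In quarter-years, 4.0, 4.25, 4.5 and 4.75 meet neither condition, and every other age from 2 to under 18 meets exactly one.

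**Size of the gap.** From 4.0 to under 5.0 years is 12 months. The covered span is (18 − 2) × 12 = 192 months, and 12 / 192 = 6.25%. This is a share of the age range, not of subjects. The documents give no age distribution, and none is assumed.

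**Size per child.** SAP 5.1.9.1 names 4 scores, and Protocol 3.7.2.3 schedules 3 visits. One affected responder with every form completed therefore has 4 × 3 = 12 score values without an assigned source. A nonresponder of that age has none, because SAP 5.1.9.1 specifies these analyses for responders.

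**After the change.** With parent report at age < 5, the conditions are age ≥ 5 and age < 5. Each age from 2 to under 18 then has exactly one source, and the whole Toddler form maps to the parent.

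**The case against.** The strongest reply is that nothing of substance follows. The SAP text chooses between reporters and contains no instruction to exclude anyone. Protocol 3.7.2.3 allows a form completed by the parent or caregiver alone. If that is the only report for a 4-year-old, there is nothing to choose between, and a sensible programmer would use it. The lower limit also looks like a slip for 4 or younger in completed years.

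Most of this is fair. It lowers the chance that data are actually lost, and it supports the proposed wording, since 4 or younger in completed years is the same as under 5. It does not make the rule complete: a child with both reports, or a program written strictly from the text, still has no answer. A fault in the PDF text is unlikely, because the other comparison sign in the same sentence is intact and both items give the same limit.

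The reply on materiality also stands. Quality of life is exploratory, few subjects were enrolled, and only summaries remain. That sets the severity at minor but does not remove the gap.

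**Conclusion.** The gap is certain from the text and appears in both items. Its importance is minor. It covers 12 of 192 months of age (6.25%), affects only responders' quality-of-life summaries, and may involve no child at all. The conclusion assumes that the rule is applied as written and that age means exact age or completed years; the result is the same for both.

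Two stronger readings are tempting, and the documents do not support them.

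- A reader might say that a third of the youngest group is lost, since 12 of the 36 months on the Toddler form is 33%. That is a share of one form's age span. It says nothing about how many subjects are affected.
- A reader might infer that the SAP also leaves the quality-of-life baseline and visit undefined. In SAP 5.1.9.1, "the change from baseline at the end of Treatment Phase A to the end of the Treatment Phase B will be compared between" the two withdrawal groups, and no questionnaire is scheduled at the end of Phase A. But that sentence names no endpoint, and its interval and model are those of the sodium analysis. If it does mean quality of life, the general baseline rule in SAP 5.1.4 and the schedule in Protocol 3.7.2.3 already point to screening as the baseline and to Day 4 as the only Phase B visit. SAP 5.1 does not require the model in any case. Nor do the documents support confining change scores to Day 4. The current text allows the change to 7 days after the last dose as well, and a Day 4 form with a 7-day recall period reaches back before the first dose. No replacement model or visit rule is needed.

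**What to change.** In SAP 5.1.9.2, items 2 and 3, change the parent-report condition from age < 4 years to age < 5 years. This follows the documents' own structure: self-report already starts at 5, the Young child form starts at 5, and the other Toddler ages already use the parent's report.

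The cost is one digit in two places. No assessment, form, visit or sample size changes. If the summaries have already been programmed, confirm which source was used for any responder aged 4 to under 5 and state it with the tables.

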5.1.10 Analysis of Pharmacokinetic Parameters

To establish similarity between the CIs for PK parameter estimates between adults and pediatrics based on PK data of clearance, the clearance data of at least 20 pediatric subjects from this trial and 81 adult subjects from an existing tolvaptan trial will be used. An analysis of variance model will be performed on the natural log transformed PK parameters using the MIXED procedure in SAS, in which only one fixed effect of subject group (pediatric and adult groups) is included in the model. From each analysis, least squares means, their difference, and the 90% CI for their difference will be derived.

Then, the antilogs of the difference and the confidence limits will provide the estimate and 90% CI for the ratio of the geometric means of the 2 treatments (pediatric vs adult).

The similarity of PK parameter estimates between adults and pediatrics will be claimed if the 90% CI for the ratio of the population geometric means—based on the analysis of the log-transformed data—is contained within the confidence limits of 0.60 to 1.40.

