time zero to infinity values were 3.48 and 5.40, respectively. Therefore, a 4-fold reduction in tolvaptan dose is recommended when initiating tolvaptan therapy in subjects using potent CYP3A4 inhibitors and a 2-fold reduction in tolvaptan dose is recommended for subjects using moderate CYP3A4 inhibitors. Lovastatin increases tolvaptan  $C_{max}$  by approximately 20% but CL/F is unchanged. Tolvaptan  $C_{max}$  and AUC calculated to the last observable concentration at time t (AUCt) are increased 1.9- and 1.6-fold, respectively, when tolvaptan is coadministered with grapefruit juice. Following coadministration with 600 mg once daily rifampin at steady state, tolvaptan  $C_{max}$  and AUCt are decreased 83% and 87%, respectively.

When 30- or 60-mg tablet doses were given following a standard high-fat, high-calorie meal, no clinically significant differences in urine output were observed.

Following multiple oral doses, the tolvaptan metabolite DM-4103 was found to accumulate. This metabolite has no pharmacological activity and has shown an acceptable toxicity profile. The metabolite has not been shown to accumulate in nonclinical toxicokinetic studies; however, in a 26-week study in rats, DM-4103 plasma concentrations greater than those expected at the dose used in this trial revealed no evidence of time-dependent toxicological effects.

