### **3.2.3 Dosing Guidelines**

Subjects will be administered tolvaptan on a formulation, age- and weight-based scale.

**Table 3.2.3-1** outlines starting tolvaptan doses and adjustments when tolvaptan is administered concurrently with potent or moderate CYP3A inhibitors. Tolvaptan doses will be reduced 75% and 50% if a potent or moderate inhibitor, respectively, is being concurrently administered. As the smallest volume of suspension that can be administered is 0.3 mL (0.3 mg), subjects weighing < 3 kg, < 6 kg and taking a moderate or a potent CYP3A4 inhibitor, or weighing < 12 kg and taking a potent CYP3A4 inhibitor may not be enrolled. Suspension should be administered with the syringes provided.

Table 3.2.3-1 Starting Tolvaptan Doses With or Without Potent or Moderate CYP3A Inhibitors				
Age/Weight	Can subject swallow a tablet?	Starting Dose: No CYP Inhibitor	Starting Dose: Moderate CYP Inhibitor	Starting Dose: Potent CYP Inhibitor
≥ 4 wk (or ≥ 44 wk adjusted gestational age) to < 2 y AND ≥ 3 kg to < 6 kg c	N/A	0.1 mg/kg suspension a,b	Not eligible for treatment	Not eligible for treatment
≥ 4 wk (or ≥ 44 wk adjusted gestational age) to < 2 y AND ≥ 6 to < 12 kg c	N/A	0.1 mg/kg suspension a,b	0.05 mg/kg suspension	Not eligible for treatment
≥ 2 y to ≤ 6 y AND ≤ 30 kg c	N/A	0.15 mg/kg suspension	0.08 mg/kg suspension	0.04 mg/kg suspension
> 6 y AND ≤ 30 kg	No	0.15 mg/kg suspension	0.08 mg/kg suspension	0.04 mg/kg suspension
> 6 y AND 20 to 50 kg	Yes	7.5 mg tablet	3.75 mg tablet	1.90 mL suspension
> 6 y AND > 50 kg	Yes	15 mg tablet	7.5 mg tablet	3.75 mg tablet

a The smallest volume of suspension that may be administered is 0.3 mL (0.3 mg), therefore dose reductions cannot be accommodated for children < 6 kg taking moderate inhibitors and for children < 12 kg taking potent inhibitors.

b Tolvaptan suspension is provided in a concentration of 1 mg/mL.

c Suspension required (pediatric subjects ≤ 6 years of age and ≤ 30 kg body weight).

Titration of tolvaptan doses can occur once daily and will be based on serum sodium levels assessed at > 20 hours following initiation of therapy and each subsequent dose; titration may not occur within 24 (± 4) hours of the previous dose. Up-titration is limited to no more than twice the previous dose.

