## **4     Restrictions**

### **4.1     Prohibited Medications**

Continuous or short term use of other medications, while not prohibited, may be restricted by the investigator because of their potential for interference with tolvaptan metabolism. Tolvaptan is a sensitive CYP3A4 substrate; plasma concentrations increased approximately 4-fold when tolvaptan was administered with the potent CYP3A4 inhibitor ketoconazole. Where appropriate dose reductions are possible, tolvaptan doses may be coadministered with potent or moderate CYP3A4 inhibitors (see [Section 2.1.1](#) and [Table 3.2.3-1](#)).

A partial list of CYP3A4 inhibitors is provided in [Table 4.1-1](#).

Table 4.1-1 List of Cytochrome P450 3A4 Inhibitors (Partial List)	
boceprevir clarithromycin clotrimazole (oral) conivaptan indinavir itraconazole ketoconazole lopinavir mibepradil	nefazodone nelfinavir posaconazole ritonavir saquinavir telaprevir telithromycin voriconazole

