## 4.2 Other Restrictions

The ingestion of pomelo, grapefruit, grapefruit juice, products containing Seville oranges, and St. John's Wort is prohibited from 72 hours prior to dosing until 24 hours post-last dose of IMP. In addition, the use of alcohol within 72 hours prior to dosing and during the trial is prohibited.

Other treatment for the purpose of increasing serum sodium, eg with urea, lithium, demeclocycline, conivaptan or tolvaptan, concurrent with dosing of trial medication or within 4 days of qualifying serum sodium assessments at screening is prohibited.

The use of saline in this population should be closely monitored. The use of hypertonic saline (3% or greater), including normal saline challenge within 8 hours of the qualifying screening serum sodium laboratory assessment is prohibited. The use of hypertonic saline (3% or greater) is prohibited during tolvaptan treatment. Routine use of hypertonic saline, while prohibited, may be considered only if used emergently (ie, with a severe symptomatic episode) and with the understanding that free water clearance may be stimulated if tolvaptan had been administered in the prior 24 hours, based on the medical judgment of the investigator.

The use of normal saline (0.9%) is allowed during screening until the beginning of Treatment Phase A; normal saline use can resume in Phase C. Subjects should no longer be on maintenance fluids containing normal saline during treatment with tolvaptan. Subjects may be administered IV solutions containing hypotonic saline (eg, half-normal [0.45%] saline), if necessary, for fluid management. The medical monitor should be contacted at any point if questions arise regarding the use of saline during the trial.

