## **6 Pharmacokinetic/Pharmacodynamic Analyses**

### **6.1 Pharmacokinetic Analysis**

Tolvaptan and metabolite plasma concentrations will be summarized using descriptive statistics (n, median, mean, standard deviation [SD], percent coefficient of variation [CV], minimum, and maximum) by dose group and time point. Plasma PK parameters, including tolvaptan  $C_{max}$ ,  $t_{max}$ ,  $AUC_{0-24h}$ , and clearance (dose divided by  $AUC_{0-24h}$ ) on Day 1, and volume of distribution on Day 1, will be summarized using descriptive statistics by dose group and age group (age [REDACTED] | [REDACTED]). These parameters will be analyzed to assess the potential effects of age, sex, race, and disease state on tolvaptan PK.

A population analysis will be performed and reported separately.

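### The pediatric-versus-adult clearance comparison has no term or exclusion for CYP3A4 co-medication, although the protocol admits inhibitor users and its own figures show large effects on clearance

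*SAP*

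**What the plan says.** SAP 5.1.10 and Protocol 7.4.2.3 fit an analysis of variance to log-transformed PK parameters, "in which only one fixed effect of subject group (pediatric and adult groups) is included in the model". Similarity is claimed if the 90% CI for the ratio of geometric means "is contained within the confidence limits of 0.60 to 1.40". The SAP plans at least 20 children against 81 adults from existing data. Neither section has an exclusion, stratum or covariate for interacting drugs.

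Children on CYP3A4 inhibitors may enroll. Exclusion criterion 3 (Protocol 3.4.3) removes only potent-inhibitor users under 12 kg and moderate-inhibitor users under 6 kg. For the others, Protocol 3.2.3 states: "Tolvaptan doses will be reduced 75% and 50% if a potent or moderate inhibitor, respectively, is being concurrently administered".

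On other drugs, Protocol 4.1 says: "Continuous or short term use of other medications, while not prohibited, may be restricted by the investigator". Protocol 4.2 adds that "St. John's Wort is prohibited from 72 hours prior to dosing until 24 hours post-last dose of IMP". No rule names rifampin or CYP3A4 inducers as a class.

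Protocol 6.1 defines clearance as dose over AUC0-24h on Day 1. It lists the covariates to be explored: "These parameters will be analyzed to assess the potential effects of age, sex, race, and disease state on tolvaptan PK". Co-medication is not among them. A population analysis is to be reported separately, with covariates not stated.

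**The concern.** The comparison is meant to show whether children clear tolvaptan as adults do. A child on a potent inhibitor contributes a clearance value that reflects the co-medication. Reducing the dose lowers dose and AUC together, so it corrects exposure but leaves dose/AUC where the interaction put it.

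Protocol 1.2.1 gives the size. With ketoconazole, the ratios for Cmax and AUC from "time zero to infinity values were 3.48 and 5.40, respectively". "Following coadministration with 600 mg once daily rifampin at steady state", AUC falls by 87%. With about 20 children, a few such values can move the geometric mean ratio and widen its interval. Similarity may then be missed when it is true, or claimed when it is false.

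**Working it through.** **Inputs.** CV of clearance 0.42, 20 children and 80 adults (SAP 4.2); 81 adults, 90% CI, limits 0.60 to 1.40 (SAP 5.1.10); interaction sizes (Protocol 1.2.1, 2.1.1 and 4.1). The number of users is not given, so the counts below are assumed, as is an adult group free of interacting drugs.

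**The plan's own figure.** Log-SD = sqrt(ln(1 + 0.42²)) = 0.403. SE = 0.403 × sqrt(1/20 + 1/80) = 0.101. SAP 4.2 states 90% power for a 95% CI within 0.71 to 1.40. Taken literally, this gives 0.83. With the 90% CI used in the analysis it gives 0.91, and exactly 20 children are needed for 90%. So n = 20 is reproduced at the 90% level. With the analysis limits of 0.60 to 1.40 and 81 adults, the chance of claiming similarity at a true ratio of 1 is 0.95.

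**Shift in apparent clearance per affected child.**
- Ketoconazole: 1/5.40 = 0.185, or 5.4-fold lower. This is AUC to infinity, whereas trial clearance uses AUC0-24h. Protocol 2.1.1 and 4.1 say concentrations rose about 4-fold, giving 1/4 = 0.25.
- Moderate inhibitors: no AUC ratio for such a drug class is given, only a 2-fold dose rule. A factor of 1/2 is inferred from it.
- Rifampin: 1/(1 − 0.87) = 7.7-fold higher.

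**Expected ratio.** With k of 20 children shifted by a factor f and a true ratio of 1, the geometric mean ratio is f^(k/20). For example, 0.185^(4/20) = 0.71.

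**Chance of claiming similarity, true ratio 1.** Simulation of 20 versus 81, pooled-variance t, 90% CI within 0.60 to 1.40:

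| Users among 20 | Ratio | P(claim) |
|---|---|---|
| None | 1.00 | 0.95 |
| 1 potent, 5.4-fold | 0.92 | 0.98 |
| 2 potent, 5.4-fold | 0.84 | 0.93 |
| 3 potent, 5.4-fold | 0.78 | 0.71 |
| 4 potent, 5.4-fold | 0.71 | 0.36 |
| 4 potent, 4-fold | 0.76 | 0.64 |
| 4 moderate, 2-fold | 0.87 | 0.97 |
| 6 moderate, 2-fold | 0.81 | 0.89 |
| 1 rifampin-type | 1.11 | 0.68 |
| 2 rifampin-type | 1.23 | 0.25 |

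Inducers do damage at lower counts because, on the log scale, the upper limit is nearer: ln 1.40 = 0.34 against ln 0.60 = −0.51. For the same reason a single potent-inhibitor user slightly raises the chance of a claim.

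**False similarity.** With a true ratio of 1.4 among unaffected children, P(claim) is 0.05 with no users, 0.41 with two potent-inhibitor users and 0.90 with four. With a true ratio of 0.6, two rifampin-type users raise it from 0.05 to 0.51.

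**Larger samples.** Twenty is a minimum. With 40 children, 15% on a potent inhibitor gives 0.87 (0.71 with 20), and 5% on a rifampin-type inducer gives 0.85 (0.68 with 20). The bias in the ratio is unchanged.

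**The case against.** The strongest reply is that the harm rests on an unknown share of users. One or two potent-inhibitor users among 20 hardly matter, moderate users hardly matter at an assumed 2-fold shift, and the smallest children on inhibitors are excluded. All of this stands and limits the size of the concern. It does not make the decision rule sound, because the trial could recruit three or four potent-inhibitor users, or a single rifampin-type user, without breaking any stated rule.

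The separate population analysis might examine co-medication. It is not said to, and it does not alter the rule in SAP 5.1.10.

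SAP 5.1 says that, after low enrollment and early termination, its efficacy analyses need not go beyond summary statistics. Section 5.1.10 is numbered under 5.1 but is a PK analysis, so it is unclear whether the comparison will be run.

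Four stronger readings are tempting but not supported:
- *That every inhibitor lowers clearance about 5-fold.* The figure is for ketoconazole only.
- *That inducers are unrestricted.* St. John's Wort is prohibited, and investigators may restrict drugs that interfere with tolvaptan metabolism. What is missing is an explicit rule naming rifampin-type inducers.
- *That inhibitor and inducer users cancel out and produce false similarity.* When the shifts roughly cancel, little bias remains and the variance rises. At a true ratio of 1.4 the false-claim rate falls from 0.05 to 0.016 with one user of each kind. Masking needs one class to predominate.
- *That summaries by dose group worsen the problem at 3.75 mg.* Under Table 3.2.3-1 only inhibitor users start on that tablet, so the group already separates them from the rest. The mixing is at 7.5 mg, which combines uninhibited 20-50 kg children with moderate-inhibitor users above 50 kg.

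**Conclusion.** The concern holds in a limited form. The similarity rule makes no provision for co-medication that, on the protocol's own figures, can shift apparent clearance about 4- to 5.4-fold down (ketoconazole) or 7.7-fold up (rifampin), and the dose reduction does not correct for this. At the minimum of 20 children, three or four potent-inhibitor users, or one or two rifampin-type users, materially lower the chance of a correct similarity claim. A predominance of either class can lift the false-claim rate well above 5%.

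The sizes assume 81 adults on no interacting drug, log-SD 0.403, adult interaction ratios carried over to children and to AUC0-24h, and the user counts shown. The defect in the plan is clear from the text. How much it would have mattered in this trial cannot be determined from the documents.

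**What to change.** In SAP 5.1.10 and Protocol 7.4.2.3, run the similarity analysis on children with no potent or moderate CYP3A4 inhibitor and no potent inducer on board through the Day 1 PK samples. Count only those children toward the 20. Summarise users separately, and do not merge them with non-users in the 7.5-mg starting group. Add CYP3A4 co-medication to the covariates in Protocol 6.1. State in the SAP whether the comparison will be run after early termination.

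The cost is a change of wording, since concomitant medication is already recorded. A few children leave the similarity set, and PK sampling may run slightly longer. With no users in the set and 20 children, the chance of a claim at a true ratio of 1 is 0.95; with 15 it is still about 0.90, so the loss is affordable.

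Whether Protocol 4.1 and 4.2 should address inducers in light of the rifampin figures in 1.2.1 is a separate matter for the sponsor to reconcile.
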